8.1.5 Exacerbation and relapse visits

Additional information on the assessments performed during TTP exacerbation and relapse is included in sections 8.1.2 and 8.1.3 respectively.

8.2 Assessment of Efficacy

8.2.1 Clinical Outcome

- Time-to-response of treatment, defined by a recovery of platelets $\geq 150,000/\mu\text{L}$. This response must be confirmed at 48 hours after the initial reporting of platelet recovery above $150,000/\mu\text{L}$ by a *de novo* measure of platelets $\geq 150,000/\mu\text{L}$ and LDH $\leq 2 \times \text{ULN}$
- Number of subjects with complete remission
- Number of (subjects with) exacerbations of TTP and time to first exacerbation of TTP. Exacerbation is defined as recurrent thrombocytopenia following a response and requiring a re-initiation of daily PE treatment after ≥ 1 day but ≤ 30 days after the last daily PE.¹
- Number of subjects relapsing of TTP (defined as *de novo* event of TTP that occurs later than 30 days after the last daily PE) for a maximum of 1 year, and time to first relapse of TTP
- Daily PE data, including serious adverse events (SAEs) related to daily PE treatment
- Neurocognitive function, as measured by a neurocognitive test battery, at complete remission and at 1 year follow up. This test will be preceded by the Glasgow Coma Score to measure the state of consciousness of the subject
- Improvement of organ dysfunction and improvement of TTP related signs and symptoms
- Total mortality within the daily PE treatment period and within the subsequent study drug treatment period (including tapering)
- Determination of biomarkers of TTP including but not limited to disintegrin-like and metalloprotease with thrombospondin repeats 13 (ADAMTS13) levels and anti-ADAMTS13 antibody titres (see also PD assessments)

8.2.1.1 Outcomes of Special Interest

8.2.1.1.1 Plasma exchange

PE is the principal therapy of this pathology. PE will be described and recorded in detail throughout the study. This includes the initial series of PE sessions, as well as any further PE sessions that may be administered after interruption of the previous session. All PE sessions arising prior to remission and ultimately within 1 year after inclusion into the study will be recorded.

The following minimum details will be required, for each PE session:

1. Start date/time and end date/time of each procedure
2. Completion as planned or interruption needed and reason thereof
3. Plasma replacement
 - a. Type of plasma product used
 - b. ABO group used
 - c. Total number of units used during the PE session
 - d. Total volume used for plasma replacement during the PE session
4. Anticoagulant administered, if any, for the PE session
5. Concomitant medication administered specifically as part of the PE procedure and during the course of the PE session will be recorded separately. Other concomitant medication, such as methylprednisone will be reported in the concomitant medication other than PE-related medication.

Medication given in response to a PE-related AE (i.e. antibiotic administration due to a central line infection) will be reported in the concomitant medication other than PE-related medication. This also includes immunosuppressive and other treatments adjunctive to PE (i.e. methylprednisone, rituximab).

8.2.1.1.2 Transfusion of RBC

Transfusion of RBC will be described by:

- Number of RBC units
- Date/time of administration
- This data is entered in the concomitant medication other than PE.

8.2.1.1.3 Peripheral and/or central blood line placement and replacement for daily PE

Each placement and replacement will be described for:

- Central or peripheral access
- Implant date/time and removal date/time of each central access
- Material used and anatomical point of entry
- Results of culture after removal

8.2.1.1.4 Supportive measures

Supportive measures will be described in concomitant medication other than PE.

8.2.1.1.5 Modified ITP bleeding score

This bleeding score is described in Section 8.3.3.

8.2.1.1.6 Neurocognitive battery

This test battery is described in the Section 8.3.6.

8.2.2 Pharmacodynamics

Sampling

Pharmacodynamic parameters listed below will be assessed by a central laboratory. Blood samples for laboratory parameters will be collected as scheduled in Table 10 (screening and baseline), Table 11 (treatment phase) and Table 13 (follow-up).

- RICO (conducted at central lab)
- vWF, including vWF:Ag and vWF propeptide (conducted at central lab)
- FVIII chromogene (conducted at central lab)

Instructions for the handling of laboratory samples are in a separate Laboratory Manual.

Labelling and shipping procedures for PD samples

Sites will receive required material for sampling before the start of the study. The tubes will be labelled and will carry the following information:

- Type of sample, e.g., blood, urine, etc.

- Study number
- Subject number
- Sample number
- Scheduled time of sampling

Instructions for the handling of laboratory samples are in a separate Laboratory Manual.

8.2.3 Laboratory Markers of Disease

Disease markers listed below will be assessed by a central or local laboratory. Blood samples will be collected as scheduled in Table 10 (screening and baseline), Table 11 (treatment phase) and Table 13 (follow-up).

- ADAMTS13 and anti-ADAMTS13 antibody titre (central laboratory)
- Cardiac marker (TnT or Tnl)
- BNP or NT proBNP
- Brain damage markers (NSE, S β 100) (central laboratory)
- PD (see Section 8.2.2 above)

8.3 Assessment of Safety

8.3.1 Safety Laboratory Monitoring

Blood samples for laboratory parameters will be collected as scheduled in Table 10 (screening and baseline), Table 11 (treatment phase) and Table 13 (follow-up).

All safety laboratory parameters will be performed at each local site laboratory. For each local laboratory, the Investigator will provide Ablynx with the name, professional degree and curriculum vitae of the laboratory director, a copy of the laboratory's certification- and the normal ranges for each parameter being evaluated in the study. These laboratory references must be forwarded to Ablynx before study start and updated whenever necessary. However, the Investigator will request that the clinical laboratory does not change any normal range during the course of the study.

Instructions for the handling of laboratory samples are in a separate Laboratory Manual.

Virus serology will be measured at screening only. The samples will be sent to the local laboratory as soon as possible after blood sampling.

Laboratory data will be transmitted electronically from the laboratory, to the study site. A print-out of the laboratory results will be added to the source documents. Each parameter outside the normal range will be assigned as H (high) or L (low) on the laboratory sheet. The

Investigator has to interpret each “outside the normal range” value as n.c.s. (not clinically significant) or c.s. (clinically significant). In the latter case the Investigator has to give a comment and the deviation is judged as an AE or SAE as appropriate.

Laboratory parameters

For all the items below the name of the laboratory, units of each parameter and normal range (lower limit of normal (LLN) and ULN) must be specified.

- Haematology
 - Full blood count, including haemoglobin, haematocrit, MCV, MCH, MCHC, full blood count including: RBC, WBC and differential blood count
 - Reticulocytes
 - Optical platelet count (if not available, can be replaced by measurement based upon impedance)
 - Immature platelet fraction (can be omitted)
- Blood chemistry
 - Glucose
 - Bilirubin (total)
 - AP
 - AST
 - ALT
 - LDH
 - CRP
 - hCG (for women, only if urine pregnancy test is not feasible or inconclusive)
 - Rheumatoid factor
 - Antinucleic acid
 - Iron, ferritin, transferrin
 - Creatinine, urea (BUN), uric acid
 - Protein, albumin
 - Na, K, Ca, Mg, Cl
- Urinalysis
 - pH
 - Specific gravity
 - Protein
 - Glucose
 - Ketones
 - Bilirubin
 - Blood

- Nitrite
- Urobilinogen
- Leukocytes
- Urine pregnancy test for female subjects (hCG only)
- Virus serology
 - HIV1 and HIV2 antibodies at screening
 - Surface antigen of HBV (HbsAg) and HCV antibodies at screening
- Coagulation variables
 - aPTT
 - PT
 - INR
 - Fibrinogen
 - vWF:Ag
 - FVIII chromogenic or alternative method (e.g. one stage clot test)
 - Lupus anticoagulant
 - Anticardiolipin antibodies (antiphospholipid)
- Blood typing (ABO and Rh) and DAT

8.3.2 Physical Examination and Vital Signs

A complete patient review and clinical assessment including vital signs will be performed at screening, during treatment phase and during follow-up, as indicated in Table 10, Table 11 and Table 13, respectively.

Blood pressure (systolic and diastolic) shall always be measured on the same arm (preferentially on the left arm). Heart rate measurements will be performed manually. Body temperature will be measured by the standard means of the investigational site. Measurements shall be recorded from the subject in the lying position after having rested for a 5-minute period.

After drug administration, inspections for vascular effects will focus on checks for bruising, haematomas, bleeding at injection and puncture sites and shaving nicks, gingival haemorrhage after brushing teeth, epistaxis and urinary blood loss or any other unusual bleeding. Specific questioning will be performed on whether subjects have experienced bleeding or bruises since the last examination.

8.3.3 Bleeding Events

Clinically relevant bleeding

Incidence of clinically relevant bleeding will be reported. Clinically relevant bleeding is defined as moderate to severe (including life-threatening) bleeding requiring urgent medical and/or surgical intervention.

Modified ITP bleeding score

Bleeding will also be measured using a modified version of the immune thrombocytopenic purpura (ITP) bleeding score. The rationale for using a modified version of the ITP bleeding score is the following. Both the WHO bleeding scale and other bleeding scales used in the frame of cardiac intervention or treatment of venous thromboembolism include bleeding or blood loss requiring transfusion of packed RBC or whole blood as a severity factor. It is common for subjects undergoing PE to need transfusions, even without apparent bleeding. The ITP bleeding score²⁷ does not include transfusion data. It is expected to be more sensitive than the other bleeding scales mentioned above. The modified ITP bleeding score is the sum of the scores for each line (Table 15).

Table 15: Modified ITP bleeding score.

Grade	0	1	2
Skin: petechiae	None	Scattered petechiae	Diffuse petechiae
Skin: ecchymosis	None	1-5 bruises	>5 bruises with size > 2cm
Oral	None	1 blood blister or >5 petechiae or gum bleeding <5 min	Multiple blood blisters or gum bleeding >5 min
Epistaxis	None	Blood when blowing nose or epistaxis <5 min (per episode)	Epistaxis >5 min (per episode)
Ocular	None	Subconjunctival haemorrhage	
Intracranial	None		Haemorrhage
Gastrointestinal	None	Blood when wiping	Blood present on stool
Urinary	None	Dipstick greater than trace	Macroscopic
Gynaecological	Normal period	Spotting outside of normal period	Bleeding greater than spotting outside of normal period, or very heavy period
Pulmonary	None	Haemoptysis	Haemorrhage

Clinically relevant findings that are observed prior to study drug initiation must be recorded on the relevant Medical History source documents page. Abnormalities in local tolerability will be reported via AE reporting throughout the trial. Clinically relevant findings found after study

drug initiation and meeting the definition of an AE (new AE or worsening of previously existing condition) must be recorded on an AE page of the source documents.

8.3.4 Cardiovascular Monitoring

12-lead ECGs will be performed at the time points specified in Table 10 (baseline), Table 11 (treatment phase) and Table 13 (follow-up). ECGs will be conducted with respect to the following procedure. Subjects will be in horizontal position during the measurements. ECGs will be evaluated and classified as normal/abnormal. In case of "abnormal", the abnormality has to be described. Heart rate, PR, QRS, QT and QTc (Bazett) will be entered into the database. Bazett is automatically calculated by the ECG apparatus and provided on the print-out. Fridericia and RR will be calculated from the available data. For the baseline ECG, one recording will be made. The 12-lead ECGs will be recorded after the subjects have rested for at least five minutes in supine position. Six limb leads, as specified by Einthoven (I, II and III) and Goldberger (aVR, aVL, aVF), and six precordial leads (V1–V6), according to Wilson, will be used. The ECG will be recorded at a paper speed of 25 mm/s and a standard calibration of 1 mV (= 10 mm). Each ECG will include the following information: identification of each lead, study number, subject number, paper speed, voltage calibration as well as date and time of the recording. This procedure will also be followed for unscheduled visits.

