4.2 Overall Study Design

This is a Phase II multicentre, single-blinded, parallel design, randomised, placebo-controlled study. The study population is symptomatic patients with acute episodes of acquired TTP, requiring treatment with PE. After confirmation of eligibility to study participation, subjects will be randomised in a ratio of 1:1 to either receive ALX-0081 or placebo as adjunctive therapy to PE (Figure 4). Subjects will be randomised prior to the start of PE treatment. In exceptional cases however (due to need or ability to start PE in a time frame which does not allow all required screening and/or baseline study procedures to be performed), a subject may be randomised after the first, single PE session, but prior to the start of the second PE session. This overall second PE session should be started within 24 hours of the end of the very first PE session, and will be considered the first PE on study.

The subjects will be followed in different phases during this study (also see Figure 5):

- Screening and baseline measurements after admission to hospital
- Treatment phase
 - Single i.v. bolus study drug administered via push injection
 - Daily PE adjunctive s.c. treatment phase
 - Post-daily PE s.c. treatment phase (including PE tapering if applicable, and study drug post-PE for 30 days after the very last PE)
- Follow-up phase

Laboratory parameters for inclusion, study conduct, safety assessments and assessments of response/relapse, re-treatment and study medication dose modification will be assessed at each local site laboratory.

[figure not shown]

Figure 4: Treatment flow chart.
First PE on study: see section 4.2

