Duration of study treatment exposure post daily PE (days): Defined as date of last dose of study treatment – date of first dose of study treatment after the daily PE period + 1

RR interval for electrocardiogram (ECG): Defined as 60,000 / Heart Rate

---

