### 6.1.5 Changes to Planned Analyses from the Protocol

- Section 4.1.2 of the protocol describes the following secondary endpoint:  
Resolution or improvement (improvement of  $\geq 1$  grade in the CTCAE v4.0 scale) of TTP-related signs and symptoms as captured on the physical examination and as adverse events.  
  
At the time of writing this Statistical Analysis Plan, it is apparent from the design of the CRF that the CTCAE grade is recorded only once per event. Therefore it is not possible to determine if or when the CTCAE grade of a particular event has improved by  $\geq 1$  grade. As a consequence, for the adverse events part of this endpoint only resolution of events (defined as having a stop date and an outcome of either 'resolved' or 'resolved with sequelae') will be considered.
- Section 4.1.2 of the protocol describes the following secondary endpoint:  
Resolution of non-focal neurological symptoms as defined by neurocognitive function at complete remission, measured by a neurocognitive test battery.  
  
The intention was to define neurocognitive function as having a CNTB average summary score immediately post hospital discharge that is equal to or higher than at Baseline. At the time of writing this Statistical Analysis Plan, it is apparent from the data for the CNTB that the majority of subjects do not have their first CNTB assessment until after they have received study treatment. The time from first treatment to first CNTB assessment is not consistent across subjects, such that a homogeneous Baseline time point cannot be defined. It is therefore not appropriate to derive this endpoint based on change from Baseline because the resulting data will have no meaningful interpretation. It has been agreed that the CNTB will be summarised by descriptive statistics at each time point for actual results only; change from Baseline will not be calculated.

- Section 4.1.3 of the protocol describes the following secondary endpoint:  
Resolution of non-focal neurological symptoms as defined by neurocognitive function at one year follow-up, measured by a neurocognitive test battery.  

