### 6.4.4 Electrocardiogram

A 12-lead ECG will be recorded after at least 5 minutes in the supine position at baseline (15minutes – 6 hours prior to PE and study drug), day 1 (4 – 6 hours post study drug), day 4 (4 – 6 hours post study drug), pre-discharge, weekly (+/- 2 days) post-discharge (during continued study drug administration), 1 month (+/- 3 days) follow-up, 2 month (+/- 7 days) follow-up, 3 month (+/- 15 days) follow-up, 6 (+/- 15 days) month follow-up, 12 (+/- 15 days) month follow-up and at any AE occurrence or other unscheduled visits.

---

If ECG is abnormal at baseline, additional ECG measurements will be taken daily during hospitalisation.

The absolute values of heart rate, PR, QRS, QT, QTc (Bazett) and RR will be summarised at baseline and each post-drug visit by treatment using the summary statistics for continuous variables. Change from baseline values will also be presented for post baseline visits.

The number and percentage of the subjects with Normal / Abnormal Not Clinically Significant / Abnormal Clinically Significant categorical ECG results will be summarised by treatment and visit.

The shifts in Normal / Abnormal Not Clinically Significant / Abnormal Clinically Significant results from baseline to all subsequent ECG readings will also be summarised by treatment and visit.

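### The protocol commits to a Fridericia QTc alongside Bazett, but the SAP summarises Bazett only and does not record the change

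*Protocol*

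**What the plan says.** Protocol Section 8.3.4 (Cardiovascular Monitoring) provides for two heart-rate corrections. Bazett comes from the machine: "Heart rate, PR, QRS, QT and QTc (Bazett) will be entered into the database". The second is to be derived: "Fridericia and RR will be calculated from the available data".

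The SAP takes up half of that second statement. Section 3 defines RR: "RR interval for electrocardiogram (ECG): Defined as 60,000 / Heart Rate". No formula for Fridericia follows, there or elsewhere in the available SAP text. The ECG parameter list in Section 5 has Bazett as its only corrected QT, and Section 6.4.4 plans the analysis on the same basis: "The absolute values of heart rate, PR, QRS, QT, QTc (Bazett) and RR will be summarised at baseline and each post-drug visit by treatment". It then adds: "Change from baseline values will also be presented for post baseline visits".

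Section 6.1.5, "Changes to Planned Analyses from the Protocol", lists three departures: the CTCAE improvement endpoint and two neurocognitive endpoints. The QTc correction is not among them.

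**The concern.** Protocol Section 10 says that the SAP will hold all the methods used to analyse the data. If the SAP is followed as written, no Fridericia summary will be produced, and no reason will be on record.

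The omission matters because Bazett and Fridericia diverge as heart rate moves away from 60 bpm. Randomisation makes heart rate comparable at baseline, but not after treatment starts, because treatment may itself change it. The trial enrols acutely ill patients ("The study population is symptomatic patients with acute episodes of acquired TTP, requiring treatment with PE") and is designed around faster recovery on ALX-0081. If heart rate follows recovery, the arms could differ in heart rate at the visits where QTc is compared. A lower heart rate in the ALX-0081 arm would pull its Bazett QTc down relative to placebo, in the direction that could offset a real prolongation. A second correction would show whether a Bazett difference depends on the formula.

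**Working it through.** The documents give no QTc figure to reproduce, so the check uses the formulas with labelled assumptions.

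**Formulas.** RR in ms = 60,000/HR (SAP Section 3). Let s = RR/1000 = 60/HR, in seconds.

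- Bazett: QTcB = QT / s^(1/2)
- Fridericia: QTcF = QT / s^(1/3)
- Ratio: QTcB/QTcF = s^(-1/6) = (HR/60)^(1/6)

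The ratio is 1.000 at 60 bpm, 1.049 at 80, 1.089 at 100 and 1.123 at 120.

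**Between-arm artefact at a visit.** Assume the same QTcF, 410 ms, in both arms. Then QTcB = 410 × (HR/60)^(1/6). The heart rates are also assumptions.

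| HR (bpm) | (HR/60)^(1/6) | QTcB (ms) |
|---|---|---|
| 70 | 1.0260 | 420.7 |
| 75 | 1.0379 | 425.5 |
| 80 | 1.0491 | 430.1 |
| 90 | 1.0699 | 438.7 |

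- 75 versus 80 bpm: 430.1 − 425.5 = about 4.6 ms
- 70 versus 90 bpm: 438.7 − 420.7 = about 18 ms

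The artefact scales with the assumed QTcF. For 70 versus 90 bpm the ratios differ by 0.0439, giving 0.0439 × 380 = 16.7 ms and 0.0439 × 440 = 19.3 ms.

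**The same example as change from baseline.** Suppose both arms start at 110 bpm, where QTcB = 453.6 ms. An arm that falls to 70 bpm shows 420.7 − 453.6 = −32.9 ms. An arm that falls to 90 bpm shows 438.7 − 453.6 = −14.9 ms. The difference is again 18 ms, with no change in QTcF in either arm.

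**Could the arms differ in recovery when an ECG is taken?** Both documents schedule an ECG on day 4. The sample-size sections assume median times to response of 3.36 days (ALX-0081) and 6 days (control). Under constant hazards (an assumption), the proportions responding by day 4 are:

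- ALX-0081: 1 − 2^(−4/3.36) = about 56%
- Control: 1 − 2^(−4/6) = about 37%

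So a fixed ECG falls where the design expects the arms to differ in recovery. Whether heart rate differs with it is a further assumption.

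**The case against.** Several points on the other side stand.

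- **Neither document prefers Fridericia.** The protocol enters Bazett in the database and also promises Fridericia. A reader might infer that the SAP replaced the agreed correction with an inferior one. The text shows only that one of two was dropped.
- **Heart rate is not documented.** No section gives heart rates in acute TTP or says that they fall with recovery. Both are plausible assumptions, no more.
- **The single-ECG gap is not the bias.** A reader might take, for example, the 35.8 ms gap at 100 bpm and an assumed QT of 340 ms (438.9 − 403.1) as the size of the problem. In a randomised comparison the artefact depends on the heart-rate difference between arms. A 5 bpm difference gives about 4.6 ms; 18 ms needs a 20 bpm difference.
- **The SAP offers some protection.** Section 6.4.4 also summarises heart rate, uncorrected QT and RR by arm and visit, so an imbalance would be visible. Categorical results and shift tables are planned, and all data are to be listed. Under Protocol Section 9.1.1, clinically significant ECG findings that are new or worsened must be reported as adverse events.
- **No QT signal is described.** Protocol Section 2.3.3 reports no treatment-related ECG effects in the toxicology programme. A reader might infer that a prolongation will be hidden, or that the artefact is larger than usual drug effects. The documents support neither.
- **The versions may differ.** The SAP covers adolescents, whereas this protocol requires age 18 or older, so the SAP may follow another protocol version. Whether that version kept the Fridericia commitment cannot be checked here.

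These points limit the size of the concern. They do not remove the mismatch between the two documents, and tables of heart rate beside Bazett do not give the reader a QTcF comparison.

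**Conclusion.** The point holds as a minor protocol–SAP inconsistency with a practical consequence. The protocol at hand promises a Fridericia QTc, and the SAP neither derives nor summarises it, nor says why. As planned, the only corrected-QT comparison between arms depends on heart rate by the factor (HR/60)^(1/6) relative to Fridericia.

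The possible artefact is a few milliseconds for a small heart-rate difference between arms and about 18 ms for a 20 bpm difference. This rests on an assumed common QTcF of 410 ms and assumed heart rates; it is an illustration, not a forecast. A difference of this kind is plausible only if ALX-0081 speeds recovery as hypothesised and heart rate follows.

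The consequence is confined to a descriptive safety table. Protocol Section 10.3 plans no formal testing of safety data.

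**What to change.** In the SAP:

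- **Section 3:** add QTcF = QT/(RR/1000)^(1/3), with RR in ms as already defined there.
- **Section 5:** add QTcF to the ECG parameters.
- **Section 6.4.4:** summarise QTcF as absolute value and change from baseline, by arm and visit, alongside Bazett.

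The mismatch does not by itself require QTcF to become the main display. If the sponsor intends to leave it out, Section 6.1.5 should say so and give the reason.

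The cost is one derived variable and one extra table row. QT and heart rate are already in the database, so no new data are needed.
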